13.1 Study Safety Assessment

The gait rehabilitation intervention proposed for this feasibility study includes several walking task components which have been adopted previously in established RA as part of a walking circuit [55] and the Otago Exercise Programme [56]. However our intervention has not been used in early RA and as such our feasibility study will seek to monitor the safety of the intervention in a small group of people with early RA before proceeding to the main trial. We anticipate that there will a very low risk of adverse effects associated with our intervention, which will be adapted according to individual needs. The study will not involve any invasive or potentially harmful procedures.

13.2 Definitions of Adverse Events

Adverse Event (AE) - Any untoward medical occurrence in a subject to whom the intervention has been administered, including occurrences which are not necessarily caused by or related to the intervention.

Serious Adverse Event (SAE) - Any adverse event or adverse reaction that a) results in death b) is life threatening Version Date: 11th Feb 2018 c) requires hospitalisation or prolongation of existing hospitalisation

- d) results in persistent or significant disability or incapacity
- e) consists of a congenital anomaly or birth defect.

f) is otherwise considered medically significant by the investigator.

13.3 Recording and Reporting AEs/SAEs

Participants will be asked at clinical visits whether or not they have experienced any adverse effects from the study intervention or study procedures. All AEs will be recorded in participant's clinical notes.

- AEs and SAEs occurring before enrollment will not be recorded or reported.
- Participants will be asked at each study visit about the occurrence of any AEs.
- All SAEs occurring within the 12 weeks of the intervention will be recorded.
- All AEs must be assessed for seriousness. SAEs must be assessed for causality, expectedness and severity.
- An SAE occurring to a research participant must be reported to the main Research Ethics Committee (REC) within 15 days of notification, where in the opinion of the Chief Investigator the event was:

"Related" that is, it resulted from administration of any of the research procedures And

"Unexpected" that is the type of event is not an expected occurrence as a result of the intervention provided.

Causality - This should be assessed by the CI or PI and should be described using the following categories:

- Unrelated to intervention
- Possibly related to intervention
- Probably related to intervention
- Definitely related to intervention

Severity - This should be assessed by the CI or PI and should be described using the following categories:

Mild:	awareness of event but easily tolerated
Moderate:	discomfort enough to cause some interference with usual activity
Severe:	inability to carry out usual activity

Details of SAE's arising during the trial should be entered in to the Non-cTIMP SAE reporting form, provided to the research sites. The site must enter details in the form and submit to the sponsor contact provided within 24 hours of first becoming aware of the event and any follow Version Date: 11th Feb 2018 Version Number: 1.2

up information should also be reported. Such events must be reported to sponsor in order to capture all potential related adverse events.

SAE forms should be completed and sent with 24 hours of becoming aware to a member of the GREAT study team at Glasgow Caledonian University, using the designated SAE form for non-CTIMPs using the designated email inbox.

The paper SAE form should be completed and emailed to: [contact]

The CI in conjunction with the local PI, will assess the SAE form to determine whether or not the event is related to the intervention and whether or not the event is an expected occurrence. Given the low risk nature of this study, we do not expect any SAEs to be related to the intervention. If the event is considered to be related to the intervention and is unexpected, the SAE will be reported to the REC within 15 days of becoming aware of the event.

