9.2. Patients with early rheumatoid arthritis will be identified from existing clinical lists/databases (depending on availability of these at participating sites) and will be invited to participate in the study using a mailshot approach. Invitation packs will include an information leaflet, a screening survey for study inclusion and exclusion criteria to indicate willingness to take part; consent to be contacted and preferred method of contact. Participants will also be provided with study recruitment personnel contact details for seeking further information. Non-responders will be sent 1 further reminder two weeks later. Upon confirmation of the patient's willingness to participate, the patient will be invited to attend a screening appointment to confirm their eligibility to participate and for the recruiting researcher to obtain written informed consent. Consented and enrolled participants will then undergo baseline outcome assessment and will be referred to the intervention clinician at the relevant site to receive the intervention.

10. Withdrawal of subjects

Participants have the right to withdraw from the study at any point for any reason. The investigator can also withdraw participants from the study intervention in the event of intercurrent illness, AEs, SAEs, SUSARs, protocol violations or any other relevant reasons. If a participant withdraws consent from further trial intervention and/or further collection of data Version Date: 11th Feb 2018 Version Number: 1.2 their data will remain on file and will be included in the final study analysis, unless requested otherwise.

11. Study schedule

This study will involve a maximum of two research-specific visits. A baseline measurements visit (including eligibility check), and a 12-week post-intervention follow-up visit for measurement of outcomes. The 12-week follow-up will ideally be undertaken at the end of the 12 week period commencing from the first clinical consultation for delivery of the study intervention. The details of study procedures for each visit are outlined below. A sub-sample of participants from the feasibility study as well as consenting intervention clinicians will be invited to participate in telephone-based interviews in order to undertake a deeper exploration of intervention acceptability, adherence, and safety.

11.1 Visit 1

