13.4 Expected Event of Special Interest

For SAE's that meet the criteria of Expected Adverse Events as detailed in the list below, completion of an SAE form is NOT required; however such events should be recorded on the appropriate CRF form as soon as possible.

For all Expected AEs details recorded on the CRF will include the onset date; whether or not it was an SAE; level of severity (from 1 mild to 3 severe); whether or not medication was required (yes/no) and the AE outcome (unknown, ongoing, resolved, and if resolved the date of resolution).

The data centre will subsequently generate SAE and AE reports for review by the TSC.

A list of expected adverse events in relation to the intervention and/or study participation (i.e. outcome assessment) is provided below:

- Transient post exercise soreness
- Post exercise stiffness
- Post-exercise fatigue
- Temporary exacerbation of disease-related inflammatory pain during exercises
- Trips, slips and/or falls during set-up of circuit, during exercises, and/or clearing away the circuit setup
- Temporary musculoskeletal pain from set-up of circuit at home
- Perceptions of new instance of disease flare resulting from undertaking gait rehabilitation circuit.

14. Intervention

There is strong evidence from the field of neurological rehabilitation suggesting that repetitive practice of walking tasks results in improvements in walking ability by improving lower limb function [50,90-92]. Preliminary evidence suggests that similar interventions are beneficial for improving walking ability in RA [51,52]. Our gait rehabilitation intervention is a complex intervention which can be described as individually tailored and progressed, which is to be supervised in clinic and practiced at home. It will consist of 3 main components in addition to usual care: -

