14.1 Supervised intervention sessions

Supervised intervention sessions will be delivered by a physiotherapist or podiatrist to guide participants on how to undertake a home-based gait rehabilitation programme. The delivery of intervention sessions will be pragmatic and flexible according to individual needs and preferences regarding additional attendances. Participants will be required to attend at least 2 face-to-face supervised intervention sessions and up to a maximum of 6 over a 12-week period. Where participants are unable to attend further supervised sessions after the first 2, telephone-based sessions will be provided as required within office hours to maintain contact, promote adherence to the home programme, and/or to provide specific advice regarding progression. The content of all contacts will be audio recorded and recorded on an intervention checklist by the therapists.

To address the physiological principles of overload and specificity, the gait rehabilitation programme will involve a 'gait circuit' comprised of an adapted set of task-specific, weightbearing, functional walking exercises previously employed in RA to target the main muscle groups used during walking [93,94]. Participants will be assessed by the clinician in order to determine baseline functional ability (i.e. can the participant complete each task?). The rationale for gait rehabilitation will be explained and gait circuit tasks will then be demonstrated by the clinician prior to an assessment of participants' competency in undertaking gait circuit tasks. Gait circuit starting levels (dose) and a plan for progression will be established. A reduced circuit will be prescribed for those unable to complete specific tasks due to specific disease -related impairments. Participants will be instructed to complete the gait circuit at home in addition to their usual activities.

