14.2 Support materials

Support for set up and completion of the gait circuit at home will be provided. Participants will be provided with a high quality illustrated educational booklet, an adherence diary and a DVD including educational material and step-by-step demonstrations of gait circuit home setup and task completion. A secure trial website allowing online access to the DVD content will also be set-up so that those wishing to use smart phones, smart televisions, tablets, and/or personal computers to access support materials via the internet may do so. Home support materials including the DVD and web support will be developed (via patient and public involvement activities) and evaluated as part of the feasibility study before being revised as required for the pilot trial and main trial phases.

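### Participants who attend only the minimum two supervised sessions have no scheduled question about non-serious or expected events between the second session and week 12

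*Protocol*

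**What the plan says.** **When participants are asked.** Section 13.3 gives two rules: "Participants will be asked at clinical visits whether or not they have experienced any adverse effects from the study intervention or study procedures", and "Participants will be asked at each study visit about the occurrence of any AEs". Section 11 limits the second rule: "This study will involve a maximum of two research-specific visits". These are baseline and the 12-week follow-up. The schedule in section 4 lists an adverse event review, apparently ticked at week 12 only.

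**How often participants are seen.** Section 14.1 says: "Participants will be required to attend at least 2 face-to-face supervised intervention sessions and up to a maximum of 6 over a 12-week period". It sets no date for the second session. For those who cannot attend after the first two, "telephone-based sessions will be provided as required within office hours to maintain contact, promote adherence to the home programme", and to advise on progression. No frequency and no event question is given for these calls.

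**What section 12.2 adds.** Clinicians record serious adverse events at each intervention session. Participants and local staff may report serious adverse events whenever they occur. The outcome assessor asks about serious adverse events at the end of the period. Non-serious expected events go on a standard CRF form, but the section does not say when participants are asked about them.

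**What must be recorded.** For each expected event, section 13.4 requires the onset date, whether it was serious, its severity, whether medication was needed, and its outcome with the resolution date. The list opens with "Transient post exercise soreness" and goes on to stiffness, fatigue, temporary pain, trips and falls around the circuit, and perceived flare.

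**What is already issued.** Section 14.2 gives each participant "an adherence diary and a DVD". No section of the protocol assigns the diary a role in recording events.

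**The concern.** Monitoring safety is a stated objective (sections 2.2.3 and 6). Section 13.1 explains that the intervention has not been used in early RA, and that its safety is to be watched in a small group before the main trial. How events are found therefore decides how well the study answers one of its own questions.

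The protocol asks for dated detail on events that are short-lived and arise largely from home exercise, but it ties the questions to attendance. Someone who attends twice early on and then exercises at home has no scheduled question about such events until week 12. By then, a day or two of soreness or a stumble while clearing away the circuit may be forgotten or wrongly dated.

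Section 13.4 also exempts listed events from the SAE form even when they are serious, so the CRF entry is their main written route. The likely result is an undercount of minor events and falls, with unreliable dates for those that are recorded.

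**Working it through.** **Inputs**
- Intervention period: 12 weeks from the first consultation (section 2.8).
- Home sessions: 3 rising to 5 a week (section 14.1).
- Face-to-face sessions: 2 to 6 (section 14.1).
- Week of the second session, w: not stated, so it is an assumption and is varied below.

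**Step 1: reproduce the plan's own exercise figures.** The basic session is a 2-minute warm-up, 18 one-minute tasks (3 sets of 6) and 17 rests of half a minute: 2 + 18 × 1 + 17 × 0.5 = 28.5 minutes, as stated. The upper limit is 6 sets × 6 tasks × 1.25 minutes × 5 sessions = 225 minutes a week, as stated. The exercise volume has been read correctly and is not in dispute.

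**Step 2: home sessions over the period.** 3 × 12 = 36 and 5 × 12 = 60. So there are 36 to 60 home sessions, against a minimum of two face-to-face contacts.

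**Step 3: share of home exercise after the second of two sessions.** At a constant weekly rate the share is (12 − w)/12. If the rate rises linearly from 3 to 5 a week, the sessions done by week w are 3w + w²/12, with a total of 36 + 12 = 48, so the share is (48 − 3w − w²/12)/48.

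| Second session at week | Constant rate | Rising 3 to 5 | Home sessions after it (3 to 5 a week) |
|---|---|---|---|
| 1 | 92% | 94% | 33 to 55 |
| 2 | 83% | 87% | 30 to 50 |
| 4 | 67% | 72% | 24 to 40 |
| 6 | 50% | 56% | 18 to 30 |
| 8 | 33% | 39% | 12 to 20 |

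At a constant rate, more than half of the home exercise follows the second session only if that session falls before week 6.

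**Step 4: the other end of attendance.** Six sessions spread evenly over 12 weeks leave gaps of 12/6 = 2 weeks, which is short enough for reasonable recall.

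**Step 5: does another provision fill the gap?** Reading clinical visits in section 13.3 to include the supervised sessions, which is the generous reading, gives these enquiry points for a minimum attender:

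| Provision | Non-serious or expected events between session 2 and week 12? |
|---|---|
| Question at clinical visits (13.3) | No visit in that interval |
| Question at study visits (13.3, section 4) | Week 12 only |
| Clinician recording at sessions (12.2) | Serious events only, and no session in that interval |
| Reporting at any time (12.2) | Serious events only |
| Telephone sessions (14.1) | Given when needed; no event question stated |
| Adherence diary (14.2) | No event use stated |

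No row supplies a scheduled question.

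**The case against.** The best defence is that the protocol keeps in touch with these participants. Serious adverse events can be reported at any time. Those who cannot attend further sessions are offered telephone sessions expressly to maintain contact, and every contact is audio recorded and entered on a checklist. A clinician on such a call may well hear about a fall or soreness. A subsample of 12 to 16 participants is interviewed on safety as well. For an intervention expected to carry very low risk, asking at visits is a defensible choice. The diary, the checklist and the CRF form are not shown, so they may already have a line for events.

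Much of this stands, and it rules out several stronger readings. A reader might infer that harms at home are covered only by recall at week 12. That is wrong for serious events, and telephone calls may bring out others in practice. A reader might also infer that participants progress without supervision, but section 14.1 leaves progression to the clinician's advice and offers calls partly for that purpose. Nor does the missing item in the Visit 2 list of section 11.2 mean that the week-12 question is lost, because sections 4 and 13.3 both require it.

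The defence does not supply a stated question on non-serious or expected events between the second session and week 12. The checklist's stated purpose in section 12.3 is to assess deviations from the intervention protocol. The interviews take place after week 12 and rest on recall too.

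**Conclusion.** The point holds for participants at or near the minimum attendance, and for non-serious and expected events. The protocol requires dated detail on these events but schedules no question about them between the second session and week 12.

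The stretch without a question covers 33% to 92% of the home exercise if the second session falls between week 8 and week 1. This assumes a constant weekly rate and no event question during telephone calls. No single value in that range should be taken as the plan's figure, because the protocol does not date the second session or say how many participants will stop at two. With six evenly spaced sessions the concern is small.

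A reader might go further and infer a bias between attendance groups, with low attenders appearing safer. The protocol does not support that as a finding: the study has a single arm, section 16 plans an analysis of all reported events, and no comparison by attendance is planned. What can be said is that minor events and falls may be under-counted or misdated.

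**What to change.** - In section 13.3, state that every contact, including telephone sessions, is an enquiry point for the listed expected events and for serious adverse events, recorded on the existing CRF form.
- Add a dated line for events and falls to the adherence diary already issued, unless it has one, and have it reviewed at Visit 2.
- Add the adverse event review from section 4 to the Visit 2 list in section 11.2. This is editorial.

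The changes use contacts and materials that already exist. The cost is a slight burden on participants and more minor events to enter.

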To monitor safety arising as a result of the intervention, serious adverse events (SAEs), and expected events will be recorded. The physiotherapists or podiatrists delivering the intervention will record SAEs during each intervention session, using a SAE reporting form according to the Glasgow CTU standard operating procedures for RCTs. Participants and the local personnel (intervention clinicians and outcome assessors) may report SAEs to the study team at any time. In addition, at the end of the intervention period the independent outcomes assessor will ask participants whether or not they have experienced SAEs over the 12-weeks intervention period. Expected events (defined as specific non-serious events that might be related to the intervention) will be monitored and recorded using a standard form as part of the case report form (CRF). These will be evaluated by the trial management group (TMG) to determine these are related to the intervention or study and will therefore be recorded as adverse events. Adverse events will then be reported to the trial steering committee (TSC). Given the study population, expected harms might include falling, fatigue, pain and post-exercise muscle soreness (see section 5. Assessment of Safety).

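### Section 13.3 asks about adverse effects of the intervention or study procedures at clinical visits, not about any adverse event, so non-serious events that a participant blames on something else may wait for recall at week 12

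*Protocol*

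**What the plan says.** Section 13.2 defines an adverse event independently of cause, "including occurrences which are not necessarily caused by or related to the intervention".

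Section 13.3 then gives two versions of the question to participants. For clinical visits: "Participants will be asked at clinical visits whether or not they have experienced any adverse effects from the study intervention or study procedures". The next sentence says that all adverse events go into the clinical notes. For study visits: "Participants will be asked at each study visit about the occurrence of any AEs".

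Serious events have their own provisions. Section 13.3 states: "All SAEs occurring within the 12 weeks of the intervention will be recorded". Section 12.2 adds: "The physiotherapists or podiatrists delivering the intervention will record SAEs during each intervention session". It also lets participants and local staff report serious events at any time, and at the end of the intervention "the independent outcomes assessor will ask participants whether or not they have experienced SAEs over the 12-weeks intervention period".

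For anticipated non-serious events, section 12.2 says: "Expected events (defined as specific non-serious events that might be related to the intervention) will be monitored and recorded using a standard form". The trial management group (TMG) then judges whether they are related.

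On assessment, section 13.3 requires every adverse event to be assessed for seriousness, but formal causality grading by the chief or principal investigator applies to serious events: "SAEs must be assessed for causality, expectedness and severity".

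**The concern.** A question about effects of the intervention asks the participant to decide on cause before mentioning the event. The definition in 13.2 does not require that step, and for expected events section 12.2 gives the decision to the TMG. Two questions of different breadth in one section also mean that an event may be elicited or missed according to the type of visit.

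This matters because safety is an explicit objective (section 6, objective 3), and section 13.1 says the intervention has not been used in early RA and is to be monitored here before the main trial. The design is single-arm (section 7), so there is no comparison group against which selective reporting would show. Under-elicitation of unattributed events would make the safety record look cleaner and tilt what is recorded towards events already believed to be related.

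Attribution is hard in this population. Section 12.2 names falling, fatigue, pain and muscle soreness as possible harms. Section 5.1 describes an increased risk of falls in RA, and section 5.2 describes gait problems driven by joint pain, stiffness and fatigue. A participant could reasonably put such an event down to the disease and answer no.

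**Working it through.** The point turns on wording and on the number of contacts. The plan states no figure that could be reproduced.

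**Step 1. Compare the conditions on cause.**

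| Provision | Section | Events covered | Condition on cause |
|---|---|---|---|
| Definition of adverse event | 13.2 | all | none |
| Recording in clinical notes | 13.3 | all adverse events | none |
| Question at clinical visits | 13.3 | adverse effects | must come from intervention or procedures |
| Question at study visits | 13.3 | any adverse events | none |
| Recording over the 12 weeks | 13.3 | serious | none |
| Recording at each session | 12.2 | serious | none |
| Assessor's question at end of intervention | 12.2 | serious | none |
| Expected-event form | 12.2, 13.4 | specific expected events | might be related; TMG decides |

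The clinical-visit question is the only elicitation question that requires the participant to attribute the event.

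**Step 2. Remove what is captured elsewhere.** Serious events are covered by three provisions without a causal condition, plus reporting at any time. Expected events are covered by the form. The items listed in 13.4 are mostly tied to exercise, to the circuit, or to a flare perceived to result from it, so an event that the participant regards as ordinary RA is not plainly on that list. What remains is non-serious events that the participant does not attribute to the study and that the form does not pick up.

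**Step 3. Count the opportunities to report those events.**

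- Study visits: at most 2 (section 11), baseline and week 12. Baseline precedes the intervention, so 2 − 1 = 1 unconditioned prompt follows its start.
- Clinical visits: the term is not defined. If it means the face-to-face intervention sessions (assumption), there are 2 to 6 over 12 weeks (section 14.1), all under the narrower question.
- The single unconditioned prompt comes at about week 12, so recall can span up to about 12 weeks.

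**Step 4. Check how firmly the week-12 prompt is specified.** The schedule in section 4 ticks an adverse event review at 12 weeks but gives no description. The itemised list for Visit 2 in section 11.2 does not include it. The assessor's end-of-intervention question in section 12.2 covers serious events. For non-serious events the prompt therefore rests on one bullet in 13.3 and one schedule row.

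**Step 5. Compare supervised with unsupervised exposure.** Section 14.1 describes a home-based programme, and section 14.1.1-style supervision is limited to the sessions counted above. The home circuit is done 3 to 5 times a week. Over 12 weeks that is 3 × 12 = 36 to 5 × 12 = 60 home sessions, assuming a constant frequency and full adherence, against 2 to 6 supervised ones. Most events during exercise would therefore be known only if the participant reports them.

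**The case against.** The strongest reply is that the safety system must be read as a whole. The sentence in 13.3 does not say that this is the only question asked. Serious events are recorded at each session without regard to cause, can be reported at any time, and are asked about at the end. Expected events have a standard form, and the TMG judges relatedness afterwards. Any adverse event is asked about at week 12, and interviews add safety information in a subsample of 12 to 16 participants. The sentence may also describe a topic rather than a script: the form and session checklist that would carry the actual prompts are not shown.

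Most of this stands, and it rules out three stronger readings that a reader might infer.

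- *That the participant's opinion screens out events before anyone on the study team can judge cause.* The study-visit question in the same section contradicts this. Formal investigator grading of causality is in any case required only for serious events.
- *That a hospital admission could go unasked, delaying expedited reporting.* The serious-event provisions in 12.2 and 13.3 carry no causal condition, so the documents do not support this.
- *That a given share of events would be missed.* The protocol gives no attribution rate. Any percentage would only be the complement of an assumed one, and it would ignore the other routes of capture.

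The reply does not remove the conflict of wording, nor does it supply another cause-free prompt before week 12 for non-serious events outside the expected-event form.

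**Conclusion.** The concern holds in a limited form. The clinical-visit question in 13.3 conflicts with the definition in 13.2 and with two statements in its own section. The consequence is confined to non-serious events that the participant does not attribute to the study. These may not be elicited at clinical visits, leaving one unconditioned prompt at about week 12.

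The number of events affected cannot be estimated from the protocol. The conclusion assumes that clinical visits are the intervention sessions and that staff ask the question as 13.3 words it. If the session checklist or the expected-event form already carries a cause-free prompt, the practical gap is smaller, but the text of 13.3 still needs to be reconciled. This is a worthwhile, inexpensive improvement to event capture, not a failure of the safety plan.

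**What to change.** Reword the clinical-visit sentence in section 13.3 to match the study-visit question. Suggested text: *At each clinical visit participants will be asked whether any untoward medical event has occurred since the last contact, whatever they think caused it.* State in the same place which contacts count as clinical visits, and use the same prompt on the session checklist.

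Leave the assessment routes as they stand: seriousness for all adverse events, causality grading by the chief or principal investigator for serious events, and TMG review for expected events. The change concerns what is asked and need not extend formal causality grading to every event.

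The cost is one reworded sentence, a short clarification of the term and one checklist line. Some more unrelated events will be recorded, each needing the seriousness assessment that 13.3 already requires.
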